10.2. Sample size

As this is an exploratory investigation with a qualitative primary outcome no formal sample size is calculated but it is evaluated that 10 subjects with an ileostomy (liquid output) will be adequate to investigate Test product A and B's ability to swell around the stoma.

10.3. Level of significance and power

The data will primarily be evaluated based on summary statistics. If explorative statistical analyses are performed a significance level of 5% will be applied.

10.4. Pass/fail criteria

This is an exploratory investigation and there is no formal success and/or fail criteria.

10.5. Interim analysis

There is no planned interim analysis in this investigation.

10.6. Statistical reason for termination of investigation

There will be no interim analysis and therefore no reason to terminate the investigation based on statistical considerations.

10.7. Deviation(s) from statistical design, method or analytical procedures

Any deviations from the statistical plan will be documented in the clinical investigation report.

11. Data management

Data management of all measurements described in this protocol are carried out by Clinical Operations, Coloplast A/S.

Data will be collected through an electronic data capturing (EDC) system on electronic Case Report Form (eCRF), a secure, internet-based case report form.

The EDC system used is [REDACTED]

The system is designed to be compliant with the FDA requirements of 21 CFR part 11. It is a validated data management system, with restricted role-based access control, allowing only qualified and trained personnel to enter the system. The system has full audit trail and electronic signature.

The principal investigator and delegate(s), and investigation monitor(s) must be trained in the system prior to getting access. The training is web-based (eLearning) and must be completed before access to the investigation is granted. The web-based training will be documented in the data management system. In addition, the data management specialist will demonstrate the system on a virtual/physical meeting. This training will be documented in the Clinical Investigation Training Log. The sponsor will be responsible for training the investigator, delegate(s) and the monitor(s).

Only the principal investigator, or delegate(s), who have completed the relevant eLearning, signed the Site Personnel Signature and Delegation List and Clinical Investigation Training Log will be authorised to enter data in the eCRF. When training is completed site personnel will initially get access to a training/sandbox database, for the site to get access to the real database as a minimum the Principal Investigator at a site the must complete.

The eCRF will be completed by the investigator, or delegate, that will perform primary data collection directly into the eCRF or drawn from source-documents and by the subject. The eCRF will be completed on a continuous basis starting from the point of enrolling the subject to final follow up. In addition, the principal investigator, using his/her personal login information, will be authorised to, and must, sign each eCRF. It will also be the responsibility of the investigator to ensure that all measurements and observations are correctly noted in the eCRF.

The investigator will keep a separate list of the subjects' ID numbers, names, and addresses in a locked room/cabinet.

The monitor, using his/her personal login information shall verify all data points and issue electronic queries for the authorised clinical site personnel to respond, as defined in the monitoring section (and monitoring plan, if created).

The Data Validation Plan describes which edit checks, range checks, and other consistence checks that will be done on the clinical data during conduct of the investigation. The Data Validation Plan will be developed in collaboration with the Clinical Manager and the Statistician and will be aligned with the monitoring section (and monitoring plan, if created).

A critical quality control will be performed by the data management team and queries issued where needed. Such queries must be resolved by the site personnel. Automated, real-time access to the data enable control on study compliance and safety assessments. A full audit trail ensures, that each user's (site personnel, monitor, sponsor, data manager) access to and actions in the system is tracked.

At the end of the study formal data review meeting(s) will be performed before the database will be locked.

The Data Management procedures are further described in the Data Management instructions.

11.1. Data collection procedure

All assessments and observations throughout the investigation for each subject must be carefully recorded in an eCRF or in a paper CRF (pCRF) during the visit or immediately after. The eCRF makes it possible to enter data right away when they are obtained. This is the preferred way of collecting data. In case this is not possible the data should be entered no later than seven days after the visit / procedure.

When subject and investigator is required to complete different sections in the CRF, it will be specified which sections the subject will fill in (using paper CRF or app solution) and which sections the investigator will fill in.

In the unforeseen situation, where site cannot establish connection to the EDC system, a paper CRF (pCRF) has been printed and supplied by sponsor.

If for some reason [REDACTED] is not available the subject must complete the questionnaire on the paper CRF, and the data must be entered into the eCRF by site personnel.

Qualitative evaluations will be registered in an Excel Sheet, that will be saved in the Data Management archive site with data management access only. Only the overall conclusions will be registered in the eCRF.

Photos and video records will be saved in the Data Management archive site with data management access only.

The remaining endpoints, assessment, backup measurements and baseline information can be entered directly into the eCRF.

11.2. Data retention

The Investigator file must be archived for a minimum period of 10 years after the final clinical investigation report has been signed.

12. Amendments to the Clinical Investigation Plan

No changes in the clinical investigation procedures shall be affected without mutual agreement between the principal investigator and the sponsor. The agreement of the changes must be documented by signing the corresponding clinical investigation plan amendments and registered in the Change Log.

All significant changes require notification to the EC and applicable regulatory authority. Substantial changes may require approval from the EC and applicable regulatory authority prior to implementation. (Example of significant change: Changes of inclusion criteria, end points or assessment methods)

13. Deviations from the Clinical Investigation Plan

Deviations to the Clinical Investigation Plan occurs when the activities during the clinical investigation do not comply with the EC approved investigation plan.

The investigator is not allowed to deviate from the Clinical Investigation Plan unless, under emergency circumstances or to protect the rights, safety and welfare of the subject(s).

If a situation occurs, that affect the rights, safety and well-being of the subject(s), the investigator is obliged to deviate from the CIP, and other regulations to protect the subject. The Investigator must inform the monitor immediately, and the Monitor will report and inform the Clinical Manager or designee immediately. Documentation with all relevant details will be completed to document the deviation and must be reported to the EC by the CM as required by local regulations.

The site will complete a protocol deviation eCRF form for all subject-related deviations and all deviations that are not related to a subject (for example, an untrained nurse performing study procedures) are reported in the Deviation Log by the investigator.

If any deviations to the investigation plan are detected during the monitoring visit, the Monitor shall ensure the site reports all subject-related deviations in the eCRF and non-subject related deviations on the Deviation log in the Investigator File. Additionally, the monitor must report any deviation noted during the visit in the Periodic Monitoring Report.

14. Device Accountability

All access to the investigational devices used in the clinical investigation is controlled by storage procedures and device accountability logs as described below. The investigational devices must only be used in this clinical investigation and only according to the CIP.

Sponsor keeps a device accountability log that states the physical location of all investigational devices from shipment of investigations devices to the investigational sites until return of or disposal.

The PI or an authorized designee keeps records documenting the receipt, use and return and disposal of the investigational devices, which includes:

- Date of receipt.
- Identification of each investigational device (batch no./serial no./unique code).
- The date(s) of use.
- Subject identification.

15. Statement of compliance

The clinical investigation is conducted in accordance with:

- Ethical principles that have their origin in the Declaration of Helsinki, 1964, Last amended at the 59th WMA General Assembly, Brazil, October 2013.
- MDR (EU) 2017/745
- ISO 14155:2020 "Clinical Investigation of medical devices for human subjects – Good clinical practices".
- Any applicable regional or national regulations will be specified in the country specific CIP.

15.1. Ethics committee and regulatory authorities

The CIP and/or other relevant documents are submitted to the appropriate EC(s). This clinical investigation will not begin until the required approval from the EC has been obtained. Any amendment to the protocol will be submitted to the same EC(s).

Sponsor will notify the EC(s) concerned of the end of the clinical investigation.

15.2. Data protection

As part of the investigation Coloplast A/S, [REDACTED] ("Coloplast") will collect and process the personal information the subject provides for the investigation ("subject personal data"). This includes identification and contact information (which may be anonymised depending on the nature of the investigation) as well as information about product usage experience and your health. Coloplast will comply with the EU General Data Protection Regulation (GDPR) and the Danish act on data protection ("databeskyttelsesloven"), including in connection with transfer of data to third countries, cf. chapter V of GDPR, Coloplast will only process the subjects' personal data:

1. To conduct the investigation and carry out related research based on subject consent (primary use), cf. articles 6(1)(a) and 9(2)(a) of GDPR,
2. To comply with applicable legal obligations to e.g. ensure reliability and safety, cf. article 6(1)(c) in conjunction with article 9(1)(i) of GDPR, and
3. If separate consent is given for secondary use of subject personal data, cf. articles 6(1)(a) and 9(2)(a) of GDPR – carry out research outside the clinical protocol to improve Coloplast's products and services, and for use in education.

Part of Coloplast's processing is carried out on third-party platforms (clinical trial databases) and certain third parties are assisting Coloplast in the processing (e.g. the investigator). Such cases will imply a transfer of your personal data to the third parties, but solely for the specified purposes and with the third parties acting on

instruction from Coloplast. Data may be collected and processed across the Coloplast network, which may entail processing of personal data outside the European Economic Area. In such cases, an adequate level of protection will be ensured by the third parties being subject to the standard contractual clauses on data protection adopted by the EU or to an EU-approved certification mechanism on data protection. For further information about this please the subject can always consult Coloplast's data protection officer (details below).

Subject personal data will be kept as long as required under applicable laws and regulations. The EU Medical Device Regulation obligates Coloplast to keep the data for a period of at least ten years after the investigation is completed, or, in the event that the device is subsequently placed on the market, at least ten years after the last device has been placed on the market. Subject personal data will be deleted at the end of the mandatory retention period.

If the subject has questions or queries regarding Coloplast's handling of personal information, the subject can always contact Coloplast's Data Protection Officer at [REDACTED] Complaints related to Coloplast's handling of subject personal information may similarly be sent to the Data Protection Officer, and the subject is also entitled to file a complaint with the relevant supervisory authority, which in the case of Denmark is the Danish Data Protection Agency (www.datatilsynet.dk).

The subject can write to [REDACTED] at any time to request:

- Access to personal data
- Correction of errors in personal data or to erase personal data
- Limit what can be done with personal data
- To receive personal data in machine-readable format (data portability).
- Withdrawal of consents the subject has given Coloplast to process personal data

15.3. Indemnity

All subjects are fully covered by Coloplast A/S insurance throughout the investigation.

15.4. Financial conditions

Coloplast A/S will compensate all investigators involved in the clinical investigation for their time and resources spent on the investigation. All financial agreements with the investigation sites involved in the clinical investigation will be specified in a sponsor investigator agreement.

The budget includes the salary to the Principal Investigator and study nurses, the cost of Test Products, transportation, and gift vouchers to the subjects. The Principal Investigator and study nurses have no financial interest in the investigation. The total budget for the investigation is [REDACTED], covering 10 participants.

16. Informed consent process

Written informed consent is obtained from all subjects participating in the investigation after thorough written and verbal information. The information is given by the investigator or his/her representative in the subjects' native non-technical language. Each subject will be fully informed about the aim of the investigation, procedures, potential risks or inconveniences and/or expected benefits, all anticipated adverse device effects and then have a minimum of 24h before deciding on participation. The subjects will be informed that their participation is voluntary and that they may leave the investigation at any time, without this having any influence on their further treatment.

The informed consent signature form includes personally dated signatures of the subject and the PI or his/her representative responsible for conducting the informed consent process. A copy will be provided to the subject.

If new information is to be given during the investigation, sponsor will inform the investigators, and the new information is given to the subjects by the investigator. If new information becomes available that can significantly affect a subject's future health and medical care that information will be provided to the subject in written form. CM is responsible for writing the information and providing the approved Subject Information and Consent Form to investigators that will further provide it to the subjects. If applicable, all affected subjects shall be asked to confirm their continuing informed consent in writing.

This procedure also applies to informed consent obtained from a subject's legal representative. The procedure cannot waive the subjects' legal rights.

17. Subject compensation

17.1. Compensation in case of injury

Product liability and No-Fault Clinical Investigation Insurance covering the duration of the clinical investigation are in place, to enable compensation in the event of an injury to a participating subject. See section 15.3.

17.2. Compensation for participating in the clinical investigation

Transport between Coloplast [REDACTED] and subjects home will be covered. Reimbursement of transport expenses are not taxable. Transport expenses will be paid in appropriate portions that justify the administration, throughout investigation period.

18. Adverse events, adverse device effects and device deficiencies

18.1. Adverse events

An adverse event is any untoward medical occurrence, unintended disease or injury, or untoward clinical signs (including abnormal laboratory findings) in subjects, whether or not related to the investigational medical device(s) or the comparator(s), or the procedures involved. The adverse event shall be marked with the intensity mild, moderate or severe. This could include events such as headache or dizziness.

18.2. Adverse device effect

An adverse event, which is related to the use of the investigational medical device, is an adverse device effect, and should be marked as unlikely related, possible related, probable related or with causal relationship on the adverse event form.

The definition of an adverse device effect includes any event resulting from insufficiencies or inadequacies in the instruction for use or any malfunction of the medical device, as well as any event resulting from use error or from intentional misuse of the device.

Table 2 lists anticipated adverse device effects that may occur.

Table 2 Anticipated adverse device effects and their likely incidence rates

ANTICIPATED ADE	INCIDENCE RATE
Peristomal skin irritation (incl. mechanical trauma and skin maceration)	< 10%
Allergic peristomal skin irritation (dermatitis)	< 1%

Temporary redness upon removal of the base plate is not considered an adverse device effect, however an abnormal development in intensity or duration should be considered as such.

18.3. Device deficiency

A device deficiency is the inadequacy of the investigational medical device or comparator with respect to its identity, quality, durability, reliability, usability, safety or performance. This includes malfunctions, use errors and inadequacy in the information supplied by the manufacturer including labelling.

Example: Inadequate welding of test product.

18.4. Serious adverse events (SAE)

A serious adverse event is an adverse event that:

- Led to death,
- Led to a serious deterioration in the health of the subject, users or other persons as defined by one or more of the following:
 - 1) a life-threatening illness or injury, or
 - 2) a permanent impairment of a body structure or a body function including chronic diseases, or
 - 3) in-patient or prolonged hospitalization, or
 - 4) medical or surgical intervention to prevent life-threatening illness or injury or permanent impairment to a body structure or a body function.
- Led to foetal distress, foetal death, a congenital abnormality or birth defect including physical or mental impairment.

This includes device deficiencies that might have led to a serious adverse event if:

- 1) Suitable action had not been taken, or
- 2) Intervention had not been made, or
- 3) Circumstances had been less fortunate.

These are handled under the serious adverse event reporting.

Planned hospitalization for a pre-existing condition, or a procedure required by the CIP, without serious deterioration in health, is not considered a serious adverse event.

18.4.1. Serious adverse device effect (SADE)

A serious adverse device effect is an adverse device effect that has resulted in any of the consequences characteristic of a serious adverse event.

18.4.2. Anticipated serious adverse device effect (ASADE)

Anticipated serious adverse device effect is any event that by its nature, incidence, severity, or outcome has been previously identified in the risk analysis report. In this investigation no SADE are anticipated.

18.4.3. Unanticipated serious adverse device effect (USADE)

An unanticipated serious adverse device effect is a serious adverse device effect which by its nature, incidence, severity or outcome has not been identified in the current version of the risk analysis report.

18.5. Medical care of subjects

Principal investigator shall ensure that adequate medical care is provided, during and after participation in the clinical investigation, to a subject experiencing an adverse event. All ongoing ADEs, SAEs, SADEs and DDs that could have led to a SAE at subject termination will be followed according to the Risk Benefit analysis (see 8.2) and will be followed until a resolution is addressed for a period of 2 months after subject termination. An ongoing adverse event at subject termination visit is documented as the current status for the adverse event and will not be followed up.

The subjects shall be informed of any new significant findings occurring during the clinical investigation, including the need for additional medical care that can be required, and of the nature and possible cause of any adverse events experienced.

18.6. Reporting and timelines

18.7. Investigator's reporting responsibilities

- PI at each site must assess all (S)AE's that occur at his/her site.
- All serious adverse events and serious adverse device effects must be reported to sponsor within 24 hours of the site becoming aware of the event.
- A device deficiency that could have led to a serious adverse event but did not because suitable action was taken, intervention had been made or because of fortunate circumstances should be reported to sponsor within 24 hours of the site becoming aware of the event.
- New findings and/or updates in relation to already reported serious events should also be reported to sponsor within 24 hours of the site becoming aware of the event.

When reporting the SAE, the relationship to the test material shall be described whether the event is considered

[figure not shown]
- **Not related**, the event has no temporal relationship with the use of the test material or the procedures.
- **Unlikely related**, the relationship with the use of the test material seems not relevant and/or the event can be reasonably explained by another cause, but additional information may be obtained.
- **Possible related**, the relationship with the use of the test material is weak but cannot be ruled out completely. Alternative causes are also possible (e.g. an underlying or concurrent illness/ clinical condition or/and an effect of another device, drug or treatment). Cases where relatedness cannot be assessed or no information has been obtained should also be classified as possible.
- **Probable related**, the relationship with the use of the test material seems relevant and/or the event cannot reasonably be explained by another cause, but additional information may be obtained.
- **Definitely related/Causal relationship**, the event has a temporal relationship with the test material use/application or procedures.

and the intensity of the event should be considered, as such:

- **Mild**, the intensity of the event is mild with no further action or intervention
- **Moderate**, the intensity of the event will lead to an action or intervention to solve the event
- **Severe**, the intensity of the event will lead to follow up on the action or intervention, as the effect of the action or intervention may not decrease the symptoms.

All above events must be reported by use of the relevant adverse event/serious adverse event/device deficiency form.

Please report to:

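### Section 18.7 defines the top and bottom relatedness grades by timing alone, so the grades overlap, and section 18.2 lists unlikely-related events as device effects

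*Combined protocol and SAP*

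**What the plan says.** Section 18.7 gives five relatedness grades, introduced by "When reporting the SAE, the relationship to the test material shall be described whether the event is considered". The two end grades are:

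- *Not related*: "the event has no temporal relationship with the use of the test material or the procedures".
- *Definitely related/Causal relationship*: "the event has a temporal relationship with the test material use/application or procedures".

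The three middle grades rest on plausibility and other causes:

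- *Unlikely*: "the relationship with the use of the test material seems not relevant and/or the event can be reasonably explained by another cause".
- *Possible*: "the relationship with the use of the test material is weak but cannot be ruled out completely. Alternative causes are also possible". Events whose relatedness cannot be assessed also go here by default.
- *Probable*: the relationship appears relevant and/or "the event cannot reasonably be explained by another cause".

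Section 18.2 states: "An adverse event, which is related to the use of the investigational medical device, is an adverse device effect". It adds that such an event "should be marked as unlikely related, possible related, probable related or with causal relationship on the adverse event form".

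Adverse events are a secondary endpoint (5.3) and are assessed in the safety population (10.1). The flow-chart in 7.2 registers AEs, ADEs, SAEs and SADEs.

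**The concern.** A relatedness scale should place each event in one grade, and the top grade should be the hardest to reach. As written, the top grade asks only whether the timing fits, which is normally a precondition for any related grade. An investigator who follows the text can defend two or three different grades for one event.

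Separately, 18.2 requires an ADE to be related to the device but admits a grade that 18.7 reserves for events with no apparent link or with another explanation. At stake are the causality grade reported for each event and the ADE, SADE and USADE labels. Section 18.5 makes follow-up depend on the label: ongoing ADEs are followed for 2 months after subject termination, while other ongoing non-serious adverse events are not.

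**Working it through.** The plan gives no figure to reproduce. The check sets the definitions side by side and passes example events through them. The plan does not define a temporal relationship; onset during wear is assumed to be one.

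| Grade (18.7) | Timing condition | Other condition |
|---|---|---|
| Not related | absent | none |
| Unlikely | none | link not relevant, and/or another reasonable cause |
| Possible | none | weak link not excluded, other causes possible |
| Probable | none | link relevant, and/or no other reasonable cause |
| Definitely/Causal | present | none |

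**Step 1: coverage.** Timing is either present or absent, so the two end grades between them already take every event. No middle grade has events of its own.

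**Step 2: serious event during wear, clear other cause, link not relevant.** *Not related* fails because timing is present. *Unlikely* is met. *Possible* fails because the link is less than weak. *Probable* fails on both limbs. *Definitely* is met. The event meets 2 grades. If the link is instead weak but not excluded, and a clear other cause is taken to satisfy the other-causes part of *Possible*, it meets 3.

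**Step 3: order of strictness.** The Step 2 event fails *Probable* and meets *Definitely*. The highest grade is therefore easier to reach than the one below it.

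**Step 4: does the overlap change the ADE label?** Not in Step 2. Every grade met there is in the 18.2 list, so if that list is followed the event is device-related whichever grade is chosen. The label can change when timing is absent: such an event with another reasonable cause meets both *Not related* (outside the list) and *Unlikely* (inside it).

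**Step 5: 18.2 against itself.** Take an event graded *Unlikely*. By the 18.2 list it is an ADE. By the 18.2 definition, read with the 18.7 wording for that grade, it is not.

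- If non-serious and ongoing, the choice decides follow-up under 18.5.
- If serious, the list makes it a SADE. Because 18.4.2 anticipates none, it could then be labelled a USADE under 18.4.3.

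**Step 6: exposure.** 10 subjects × 2 products = 20 completed wears, and 20 × 4 hours = 80 hours of wear, before counting any partial wears by subjects who are replaced. Few events can be expected to fall in that time.

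**The case against.** The strongest reply is that 18.2 sets a conservative threshold, with every grade except *Not related* counting as an ADE. On that reading the grades that count are already fixed and the wording is merely loose. This is plausible, but the text does not say so, and the sentence defining an ADE points the other way. The reply also leaves the 18.7 overlap in place.

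It can also be said that the word *Causal* in the label conveys the missing criterion, and that investigators will use judgement. Judgement will probably avoid absurd grades, but the definition tells the investigator how to grade, and it contains only timing. The default to *Possible* helps only where relatedness cannot be assessed, which is not so when both the timing and the other cause are known.

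A reader might infer that non-serious events have no usable scale, since the definitions are introduced for SAEs. That goes too far. Section 18.7 also requires the PI to assess serious and non-serious events alike, 18.2 reuses most of the grade names, and the adverse event form, which is not reproduced, may carry definitions. What stands is that the protocol does not state that one scale applies to all events.

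A reader might also infer that a relabelled event would visibly shift an ADE proportion for a product. The documents do not support this. The Step 2 event stays within the listed ADE grades, and no planned estimate uses the split between AEs and ADEs.

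**Conclusion.** The point holds as a minor defect in stated definitions. Read literally, the 18.7 grades are not mutually exclusive, the top grade lacks a causal criterion, and an event during wear can never be *Not related*. Section 18.2 conflicts with its own definition over *unlikely related*.

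The effect is confined to the causality grade and the labels that depend on it, including the follow-up boundary in 18.5, where over-grading would only extend follow-up. It does not reach the primary endpoint or the total number of adverse events. A reader might infer that serious events could go unreported; they would not. All SAEs go to the sponsor within 24 hours and to the ethics committee within 7 calendar days, or 2 where there is imminent risk, whatever their relatedness.

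No probability of an affected event is given, because the documents contain no background rate of coincidental events. The rates in Table 2 of 18.2 are for anticipated device effects. The conclusion rests on a literal reading and on treating onset during wear as a temporal relationship.

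**What to change.** Reconcile 18.2 and 18.7:

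1. Add to *Causal relationship* a criterion beyond timing, such as no other reasonable cause together with an effect consistent with the product or procedure, so that it is stricter than *Probable*. Allow an event with an established other cause to be graded *Not related* even when it occurs during wear.
2. Make the grades mutually exclusive, for example by stating that the first grade met in a fixed order applies. Keep the existing default to *Possible* when relatedness cannot be assessed. The order has to test *Causal* before *Probable*; otherwise an event with no other reasonable cause always stops at *Probable*. One workable order is *Not related*, *Causal*, *Probable*, *Possible*, *Unlikely*.
3. State that the same scale applies to all adverse events and, before database lock, which grades count as an ADE. If the conservative threshold is intended, say so and align the ADE definition with it.

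The cost is wording in two sections and in the adverse event form guidance, plus the amendment steps in sections 12 and 15.1. No further data collection is needed.
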